6.1 Population characteristics

Summary statistics (arithmetic mean, standard deviation, median, minimum and maximum for quantitative variables) will be presented. Frequency tables for qualitative data will be provided. Descriptive statistics will be provided for all data combined and for each age cohort. Data from children received standard of care study treatment (i.e. randomized in the study before Protocol Amendment 4 coming into effect) will be summarized as separate treatment group.

6.1.1 Demography, medical history, populations for analysis

Age, sex, race, ethnicity, weight, height, body mass index, systolic and diastolic blood pressure at baseline will be described by appropriate summary statistics. Medical history findings will be summarized using Medical Dictionary for Regulatory Activities (MedDRA) Primary System Organ Class / High Level Term / Preferred Term.

6.1.2 Prior medication for treatment of index venous thrombosis

In the tabulation of prior medication of index event all anticoagulants will be tabulated that were categorized as prior medication. Type of initial treatment of the index event and duration of initial treatment will be summarized by descriptive statistics. If fondaparinux was categorized as LMWH pre-treatment of index thrombosis by the investigator, it will be grouped to fondaparinux for the purpose of tabulation. Duration of pre-treatment for the patients on rivaroxaban study medication will be calculated as $\min(\text{start of rivaroxaban, stop date} + 1 \text{ day}) - \text{start date}$. Duration of pre-treatment for patients randomized to standard of care study medication before Protocol Amendment 4 will be calculated as $\min(\text{date of IxRS assignment, stop date} + 1 \text{ day}) - \text{start date}$ and summary statistics will be presented separately.

6.1.3 Description of the index venous thrombosis

Location(s) of index venous thrombosis as specified by the investigators and as adjudicated by the CIAC will be tabulated overall and by age group.

6.1.4 Concomitant medication

All concomitant medications will be displayed using WHO-DD, by first (anatomical main group) and second level of the ATC code (therapeutic main group).

6.1.4.1 Tabulation of concomitant antithrombotics started after stop of study medication

Concomitant antithrombotics that started on the stop day of study medication or later will be grouped first by the fourth level of their ATC codes (B01AA: Vitamin K antagonists, B01AB: Heparin group, B01AC: Platelet aggregation inhibitors excluding heparin, B01AD: Enzymes, B01AE: Direct thrombin inhibitors, B01AF: Direct factor Xa inhibitors, B01AX: Other antithrombotic agents) or if that is not available, by the third level (B01A: Antithrombotic agents). The second group will be the generic names that are reported using the codes for DRECNO where DSEQNO1=01 and DSEQNO2=001, except Certoparin, see below. The rows in the tables will be sorted first by ATC class (code order) then by generic name codes.

Note that certain medications can be coded by more than one DRECNO code. There are medications with same active ingredient, but different salt or ester component or with multiple ingredients may have different DRECNOs which may lead to tabulations of that active compound in different categories. If applicable, Certoparin sodium coded as DRECNO="016918" will be recoded to DRECNO="008896" and DSEQNO1="02" and DSEQNO2="017" to tabulate these medications under the drug name "CERTOPARIN SODIUM [HEPARIN-FRACTION, SODIUM SALT]".

6.2 Bleeding analysis

All bleeding analyses will be performed on the safety analysis set based on the outcomes confirmed by the CIAC. Bleeding events that occurred during study treatment or within 2 days after stop of study medication (i.e. treatment-emergent) will be summarized. Bleeding events observed more than 2 days after stop of study medication will be described separately. Individual listings of major and clinically relevant non-major bleeding events will be provided.

Incidence proportions (number of children with outcome by number of children at risk at start of study medication) will be presented for the primary safety outcome, for major bleedings, for all confirmed bleedings and components for pooled data and for each age stratum and by baseline presentation of venous thrombosis for the rivaroxaban group and for the standard of care group (randomized before Protocol Amendment 4) separately.

6.3 Efficacy

All efficacy analyses will be performed on the full analysis set population based on the outcomes confirmed by the CIAC. Incidence proportions will be calculated for the efficacy outcomes (see Section 3.3) overall and by age stratum for the rivaroxaban group and for the standard of care group (randomized before Protocol Amendment 4) separately. The analyses described above will include events up to the end of intended study treatment (30 days after study medication assignment) regardless of the actual stop date of study medication.

In addition if there is at least one confirmed recurrent event in the corresponding time period, the analyses described above will be performed counting only events that occurred during study treatment or within 2 days after stop of study medication (i.e. treatment-emergent) on the safety population as well.

Proportion of events that occurred more than 2 days after stop of study medication up to 30 days will be described (denominator: number of subjects entering the observational period) if there is at least one confirmed recurrent event in the corresponding time period.

In addition, all descriptive efficacy analyses will be performed on the per protocol population as a supportive analysis.

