Inclusion/exclusion criteria (continued)	10. Concomitant use of strong inducers of CYP3A4, i.e. rifampicin, rifabutin, phenobarbital, phenytoin and carbamazepine 11. Hypersensitivity or any other contraindication listed in the local labeling for the experimental treatment 12. Inability to cooperate with the study procedures 13. Previous enrollment to this study 14. Participation in a study with an investigational drug or medical device within 30 days prior to Visit 2. ¹³
Primary outcome	Composite of major and clinically relevant non-major bleeding
Secondary outcome	Composite of all recurrent venous thromboembolism and asymptomatic deterioration on repeat imaging; results of pharmacokinetics (PK) / pharmacodynamics (PD).
Statistical Analysis Plan	
The incidence of the composite of major and clinically relevant non-major bleeding and the incidence of symptomatic recurrent venous thromboembolism, and asymptomatic deterioration in the thrombotic burden on repeat imaging will be summarized descriptively.
 
Quantitative data will be described by summary statistics and presented by age.
 
Results of PK/PD analyses will be assessed descriptively. ¹⁴

¹³ Comparator arm was removed via Amendment 4 (see Section 16.2.2.2)

¹⁴ Statistical Analysis Plan modified via Amendment 4 (see Section 16.2.2.2)

Figure 1–1: Flow chart

	Screen ^a	Treatment period			30 day post study treatment contact	
Visit	1	2	3	4	5	
Days	Day -60 to Day -10	Day 1	Day 15 ± 5 days	Day 30 ± 3 days	Day 60 ± 7 days	
Obtain informed consent	•					
Check in-/exclusion criteria	•					
Obtain demographic data	•					
Check medical history	•	•				
Record anticoagulant medication	•	•				
Obtain height/length, and blood pressure	•					
Obtain body weight	•	•				
Check Hb, platelets, creatinine, ALT, bilirubin		• ^b				
Send baseline adjudication package	•					
Review the CIAC decision for index thrombotic event for final eligibility ^c		•				
Re-confirm in-/exclusion criteria ^c		•				
Provide patient details to IxRS	•					
Dispense study medication		•				
Instruct how to take study medication		•				
Provide study booklet		•				
Provide Rivaroxaban Oral Suspension Handling Guidelines to parents		•				
Record all concomitant medication		•	•	•	•	
Check for study outcomes ^d			•	•	•	
Check adverse events		•	•	•	•	
Check Hb, platelets, ALT, bilirubin				•		
Check drug accountability and compliance ^e			•	•		
Repeat imaging and send adjudication package				•		

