6.1 Study visits - amended

The study has 5 planned visits (see [Figure 1–1](#)).

Visit 1 is a screening visit and will be a hospital visit. This visit is to identify potential eligibility of children who are treated with anticoagulants for confirmed symptomatic or asymptomatic venous thrombosis. This visit will take place 60 to 10 days before Visit 2.

Visit 2 is the first study drug administration day and will be a hospital visit. Eligible children will receive rivaroxaban for 30 days.

Visit 3 and Visit 4 are the treatment and end of treatment visits, respectively. These visits will be hospital visits which will take place at Day 15 ± 5 days, and Day 30 ± 3 days, respectively. At visit 2, 3 and 4, PK/PD blood samples will be drawn. At Visit 4, the study medication will be stopped. After cessation of study treatment, it is at the investigator's discretion to continue with anticoagulation, as needed. Repeat imaging will be obtained if applicable.

Visit 5 is the 30 day post treatment contact visit and will be a hospital visit or a telephone contact. It will take place at Day 60 ± 7 days. This visit will be the last study visit.

In children who prematurely discontinue study medication, visit 5 will take place 30 ± 7 days after premature discontinuation.³⁴

6.2 Visit 1 - Screening visit at 60 to 10 days before Visit 2 - amended

The parents/legal guardians will be given explanation about the study and will be given sufficient time to consider participation of their child in the study. Parents/legal guardians who are willing to have their child participating in the study will be asked to sign an informed consent form.

Screening will only be performed after having received informed consent. Children who pass the screen of inclusion and exclusion criteria can be enrolled into the study.

Then demographic data, medical history, height/length, blood pressure and anticoagulant medication will be collected.

The images of the index venous thrombotic event need to be collected and the adjudication package needs to be completed and sent to the central adjudication office. The CIAC will assess the images and will inform the investigator about their decision.

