- Obtain blood sample for hemoglobin, platelets, ALT and bilirubin
- document the exact time of drug intake on the day prior to visit 4 and document the volume and type of fluid used to predilute the rivaroxaban oral suspension, as well as the volume and type of fluid taken after the study drug administration
- document the time and type of meal the child took 2 hours before, during and after study drug administration on the day prior to Visit 4.
- at 10 – 16 hr after last drug intake, collect the PK blood sample followed by the PD blood sample
- document the exact time of blood sampling for PK/PD
- Perform drug accountability and assess compliance
- Check changes in concomitant medications.
- Update eCRF
- Repeat imaging with ultrasound should be obtained if applicable. If repeat imaging can be done with MRI or MR angiography, this should be done only if sedation and/or general anesthesia are not required. Other modalities of imaging, e.g. CT (angiography) scan or contrast angiography, will be obtained only if the repeat test was planned independently of the study. A repeat imaging adjudication package needs to be compiled and sent to the adjudication office.

If a child discontinues study treatment permanently before visit 4, visit 4 will still need to take place:

- Check for potential study outcomes. If a suspected study outcome occurred, an adjudication package needs to be compiled and sent to the adjudication office
 - Check for adverse events. If an adverse event occurred, update the eCRF
 - Perform drug accountability and assess compliance
 - Check changes in (concomitant) medications
- No blood sampling for PK/PD, or for hemoglobin, platelets, ALT or bilirubin, is required.^{40, 41}

⁴⁰ Section modified via Amendment 1 (see Section 16.1.2.5)

⁴¹ Section modified via Amendment 4 (see Section 16.2.2.29)

6.6 Visit 5 - 30 day post treatment contact at Day 60 (+/- 7 days)

This visit or telephone contact is to document what happens to children during the 30-day post study treatment period. Therefore, this visit or telephone contact will take place at Day 60 \pm 7 days in children who completed the study treatment.

However, in children who prematurely discontinue study medication, this visit will take place 30 \pm 7 days after premature discontinuation.

- Check for potential study outcomes. If a suspected study outcome occurred, an adjudication package needs to be compiled and sent to the adjudication office.

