3.3 Outcomes

- The primary safety outcome is the composite of major bleeding and clinically relevant non major bleeding.
- Other safety outcomes:
 - all deaths
 - other vascular events (myocardial infarction, cerebrovascular accident, non-CNS systemic embolism).
- Efficacy outcomes:
 - Symptomatic recurrent VTE (composite of DVT and fatal or non-fatal PE)
 - Composite of symptomatic recurrent VTE and asymptomatic deterioration on appropriate imaging test

All index venous thrombotic events, and all suspected recurrent venous thromboembolic events, asymptomatic deterioration in the thrombotic burden on repeat imaging, bleeding, other vascular events and deaths that occur after visit 2 including the 30 day post treatment period, will be evaluated by a CIAC, which will be provided with all relevant documentation related to the events. Adjudication results will be the basis for the final analyses.

For further details see Sections [6.8](#), [6.11](#) and [6.14.2](#) of the Integrated Protocol as well.

4. General Statistical Considerations

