5.1 Assignment of analysis sets

Final decisions regarding the assignment of subjects to analysis sets will be made during the review of study data and documented in the final list of important deviations, validity findings and assignment to analysis set(s) (see Section 4.6).

Full analysis set: This analysis set will include all enrolled children (except screening failures).

Safety analysis set: This analysis set will include all enrolled children who received at least one dose of study medication.

Per protocol set: This population includes all enrolled children who had at least 25 days study treatment. Children who discontinued study treatment earlier than 25 days due to an efficacy or bleeding outcome or due to death or due to a procedure defined in the study protocol or withdrew consent will not be excluded from the per protocol set. Children with a calculated compliance less than 50% will be excluded from the per protocol set, calculated

compliance between 50% and less than 80% and greater than 120% is considered as minor protocol deviation. These definitions are considered as clarifications to the definitions in the study protocol. The per protocol set may also exclude other major protocol deviations. Further details will be specified in the in the Protocol Deviation Document and in the Validity Review Report.

In addition to the analysis population defined in the study protocol, the following population will be used as well.

All subjects with at least 1 PK sample in accordance with the PK sampling strategy will be included in the PK analysis (PK analysis set).

All subjects with at least 1 blood sample for clotting parameters in accordance with the PD sampling strategy will be included in the PD analysis (PD analysis set).

Listing only set: This population includes all screening failures.

6. Statistical Methodology

Treatment groups will be displayed as study medication administered.

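### A child with no repeat image counts by default as free of asymptomatic deterioration, so the full-analysis-set composite can be understated through that component but never overstated

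*SAP*

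**What the plan says.** SAP 3.3 lists two efficacy outcomes: symptomatic recurrent VTE on its own, and the "Composite of symptomatic recurrent VTE and asymptomatic deterioration on appropriate imaging test". SAP 6.3 sets the population and the source of events: "All efficacy analyses will be performed on the full analysis set population based on the outcomes confirmed by the CIAC". It asks for incidence proportions overall and by age stratum. SAP 5.1 defines the full analysis set as every enrolled child who is not a screening failure; having a repeat image is not a condition.

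Protocol 6.5 (Visit 4) limits when the image is taken. "Repeat imaging with ultrasound should be obtained if applicable"; MR is done only when neither sedation nor general anaesthesia is needed; CT or contrast angiography "will be obtained only if the repeat test was planned independently of the study".

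Two SAP provisions come near the problem:

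- SAP 4.3 reports the number of missing repeat images, for the rivaroxaban group and separately for the earlier standard-of-care children, and puts missing data in the subject listings. Its imputation rules concern dates only.
- SAP 6.3.1 is a sensitivity analysis for children not followed to Day 30. It models recurrence of VTE and runs only if at least one recurrence has been confirmed.

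For children who stopped treatment early, the flow chart (Protocol Figure 1-1) lists "Repeat imaging and send adjudication package" at Visit 4 and Protocol 6.1 says "Repeat imaging will be obtained if applicable", both without exemption. Protocol 7.10 keeps the visits in order to collect outcomes. The early-discontinuer list in Protocol 6.5 does not mention imaging, and its waiver names other items: "No blood sampling for PK/PD, or for hemoglobin, platelets, ALT or bilirubin, is required".

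**The concern.** A symptomatic recurrence brings itself to attention: Protocol section 3 sends suspected outcomes for confirmatory testing. Asymptomatic deterioration is found only if someone looks. Dividing confirmed events by all enrolled children treats a child who was not examined like a child who was examined and found unchanged.

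The resulting error has one direction. A missing image can hide a deterioration but cannot create one. Missing images are also foreseeable, because the protocol itself limits each imaging method, and the sedation condition applies to children under 6 years.

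Asymptomatic deterioration is a stated secondary objective, and Protocol 1.3 makes later studies depend on there being no evidence of lost efficacy. A result of 0/20 that includes unexamined children is weaker support for that step than it appears, and the age strata of 10 are affected more. The dropout analysis does not help: a child who completes follow-up without an image is outside it, and it does not run when there are no recurrences.

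**Working it through.** **Inputs.** N = 20 on rivaroxaban, 10 per age group (Protocol 4.1, SAP 3.1), taken here as the full-analysis-set size. The interval method is the 95% Blyth–Still–Casella interval of SAP 9.1. M, the number of unimaged children, is not in the documents; M = 2, 4, 8 and 12 is an assumed range.

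**Step 1: reproduce the plan's figures.** Casella's refinement of the exact limits at n = 20 gives 0.0–15.4% for 0 events, 0.3–23.1% for 1, 1.8–31.5% for 2, 4.2–36.1% for 3 and 7.1–41.1% for 4. These match all five rows of SAP Table 9-1 to within grid rounding.

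**Step 2: direction.** The observed deteriorations are the children who both deteriorated and were imaged, a subset of all who deteriorated. With a fixed denominator, observed/20 ≤ true/20 whatever links imaging to outcome. If imaging is unrelated to outcome and the true rate is d, the expected reported rate is d × (20 − M)/20. For d = 10% this is 9.0%, 8.0%, 6.0% and 4.0% at M = 2, 4, 8 and 12.

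**Step 3: size, all ages.** The columns use the same interval at n = 20 − M, the proportion 1/(20 − M), and the composite bounds x/20 to (x + M)/20, where x is the number of confirmed efficacy events (here 0).

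| Imaged | M | 0 deteriorations: upper limit | 1 deterioration among imaged (95% interval) | Composite bounds, x = 0 |
|---|---|---|---|---|
| 20 | 0 | 15.4% | 5.0% (0.3–23.1%) | 0% |
| 18 | 2 | 17.3% | 5.6% (0.3–26.0%) | 0–10% |
| 16 | 4 | 19.8% | 6.3% (0.3–29.9%) | 0–20% |
| 12 | 8 | 23.6% | 8.3% (0.4–34.9%) | 0–40% |
| 8 | 12 | 34.9% | 12.5% (0.6–50.0%) | 0–60% |

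SAP 6.3 plans proportions without limits. The limits are shown only to indicate how much information the imaged children carry.

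**Step 4: size, one age group of 10.** With no events, the upper limit is 26.7% if all 10 are imaged, and 34.9%, 40.2% or 52.7% if 8, 6 or 4 are.

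**Step 5: what the planned count allows.** From the total of missing images a reader can approximate the overall evaluable rate. The count is not planned by age group (SAP 6.6.1 extends age-cohort reporting to sections 6.1, 6.2, 6.3 and 6.5.1, not to 4.3) and is not crossed with confirmed events. Age-group rates and exact bounds therefore cannot be derived from it.

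**The case against.** The strongest counter-argument is that the SAP does not hide the problem. It reports how many images are missing and places missing data in the subject listings. If imaging status appears there, a reader could match about 20 children to age group and events by hand. That depends on the case report form, which is not available here, and a listing does not correct a reported proportion. What stands is that the gap lies in the summary analysis and the raw information may well exist.

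It is also true that SAP 6.3 never says unimaged children are non-events. The only definition of an incidence proportion is in SAP 6.2, for bleeding. The classification is the default result of the stated population and event source. A rule in the adjudication manual, the Protocol Deviation Document or the Validity Review Report cannot be excluded; there is none in the protocol or SAP.

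The size is assumed throughout, and nothing in the documents supports 8 or 12 unimaged children in particular. The outcome is secondary and descriptive, the primary objective is bleeding, and symptomatic recurrence is reported separately and is not affected this way. These points limit the weight of the concern but leave the one-way error in place.

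The early-discontinuer passages can be read together as imaging not being waived. They are unclear rather than flatly contradictory, and that point is separate from the analysis issue.

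**Conclusion.** The concern holds. As the plan is written, an unimaged child can only lower the asymptomatic-deterioration component and, through it, the composite. The bias is zero if no unimaged child deteriorated and small if imaging is nearly complete.

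With a few children unimaged the change is visible: at 4 of 20, a reported 0% is compatible with up to 20% in the worst case, and the upper limit among those imaged is 19.8% rather than 15.4%. The figures rest on a full analysis set of 20 and assumed numbers imaged; the direction does not depend on the number imaged. The change should be made, but the primary safety analysis does not depend on it.

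**What to change.** Keep the full-analysis-set result. Add to SAP 6.3, overall and by age group, and whether or not a recurrence is confirmed:

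- **(a)** Asymptomatic deterioration as events over children with an evaluable baseline and repeat image, with that denominator printed.
- **(b)** The composite among children who have an evaluable repeat image or a confirmed efficacy event, so that no symptomatic or fatal event is lost. Label it a sensitivity analysis: keeping unimaged children only when they have an event can overstate the rate.
- **(c)** Best-case and worst-case bounds, counting unimaged children without a confirmed event first as non-events and then as events.

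Items (a) and (c) are the essential ones. Record the change through the amendment or supplement route in SAP 4.6. Separately, reconcile Protocol Figure 1-1 and sections 6.1, 6.5 and 7.10 on whether repeat imaging applies at Visit 4 to children who discontinued early.

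The cost is a few table rows from data already collected. The drawback is less favourable reported figures, and wide worst-case bounds if many children are unimaged.

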6.4 Visit 3 - Treatment visit at Day 15 (+/- 5 days) - amended

- Check for potential study outcomes. If a suspected study outcome occurred, an adjudication package needs to be compiled and sent to the adjudication office.
- Check for adverse events.
- Administer the next rivaroxaban dose and document the volume and type of fluid used to predilute the rivaroxaban oral suspension, as well as the volume and type of fluid taken after the study drug administration.
- Document the exact time of drug intake and type of meal the child took 2 hours before, during and after drug administration
- Complete the Taste-and-Texture Questionnaire for children older than 4 years
- At 2 – 8 hr after drug intake, collect a post-dose PK blood sample followed by the PD blood sample
- Document the exact time of blood sampling for PK/PD.
- Perform drug accountability and assess compliance
- Check changes in concomitant medications
- Update eCRF.
- Inform that on the day before visit 4
 - the evening dose of rivaroxaban should be taken as late as possible (i.e. closely before the child goes to bed) and medication should not be taken on the day of visit 4
 - 1) to document in the study booklet the exact time of the last dose taken on the day before Visit 4, 2) the exact time and type of meal the child took 2 hours before, during and after study drug administration, 3) the volume and type of fluid used to predilute the rivaroxaban oral suspension and 4) the volume and type of fluid taken after the study drug administration. ^{38, 39}

If a child discontinues study treatment permanently before visit 3, visit 3 will still need to take place:

- Check for potential study outcomes. If a suspected study outcome occurred, an adjudication package needs to be compiled and sent to the adjudication office
- Check for adverse events. If an adverse event occurred, update the eCRF
- Perform drug accountability and assess compliance
- Check changes in (concomitant) medications
- No blood sampling for PK/PD is required.

³⁸ Section modified via Amendment 1 (see Section 16.1.2.4)

³⁹ Section modified via Amendment 4 (see Section 16.2.2.28)

6.5 Visit 4 - End of study treatment visit at Day 30 (+/- 3 days) - amended

No study medication should be taken anymore.

- Check for potential study outcomes. If a suspected study outcome occurred, an adjudication package needs to be compiled and sent to the adjudication office
- Check for adverse events.

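### SAP 6.3 closes the main efficacy window at Day 30 or 31, but the Visit 4 scan may be done up to Day 33, so asymptomatic deterioration on a compliant late scan can miss the main composite (minor)

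*SAP*

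**What the plan says.** **Outcome.** SAP 3.3 lists two efficacy outcomes. The second is "Composite of symptomatic recurrent VTE and asymptomatic deterioration on appropriate imaging test".

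**Main window.** SAP 6.3 calculates incidence proportions on the full analysis set, overall and by age stratum. It then limits them: "The analyses described above will include events up to the end of intended study treatment (30 days after study medication assignment"), whatever the actual stop date. The per-protocol repeat has no window of its own: "all descriptive efficacy analyses will be performed on the per protocol population as a supportive analysis".

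**Scan timing.** Protocol 6.1 makes Visit 2 the first dosing day (Day 1 in Figure 1-1) and has Visits 3 and 4 "take place at Day 15 ± 5 days, and Day 30 ± 3 days, respectively". Repeat imaging is marked only at Visit 4 in Figure 1-1. The Visit 4 instructions in Protocol 6.5 read "Repeat imaging with ultrasound should be obtained if applicable".

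**Other analyses in SAP 6.3.** A treatment-emergent count on the safety set, running to 2 days after stop, opens with a condition: "In addition if there is at least one confirmed recurrent event in the corresponding time period". For later events, "Proportion of events that occurred more than 2 days after stop of study medication up to 30 days will be described", with children entering the observational period as denominator and the same condition attached.

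**The concern.** Asymptomatic deterioration produces no symptoms, so in this design it will normally be found on the Visit 4 scan. The counting window and the visit window were set separately and do not match: one ends on a fixed day, while the other allows three days after Day 30. No SAP rule clearly brings a compliant late scan into the main count.

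A confirmed component of the composite, found on a scan done as the protocol allows, could therefore be missing from the headline proportion. The error runs in one direction only: it can lower the reported incidence but not raise it. The origin of the window is also left to the programmer, because *study medication assignment* is defined nowhere and Protocol 5.6 (Treatment assignment) is marked not applicable since Amendment 4.

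**Working it through.** The SAP gives no figure for this point, so the check is a calendar count.

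**Inputs**
- Day 1 = Visit 2 (Protocol 6.1, Figure 1-1).
- Visit 4 = Day 30 ± 3 (Protocol 6.1).
- Window = 30 days after assignment (SAP 6.3).
- Planned children = 20, 10 per age group (Protocol 4.1).

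**1. Which date is the origin?** SAP 4.3 replaces a missing study-drug start date by the IxRS assignment date, and moves an unexplained earlier start forward to it. It also ends prior anticoagulants with a missing stop date on that day. These rules make sense only if IxRS assignment falls at or near the first dose. Figure 1-1 also places dispensing at Visit 2. So Visit 2 is the supported reading, although the SAP never equates the two terms.

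**2. Cut-off.** Elapsed days: 1 + 30 = Day 31. With Day 1 counted: 1 + 30 − 1 = Day 30.

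**3. Permitted scan days.** 30 − 3 = 27 to 30 + 3 = 33, which is 7 days.
- Cut-off Day 31: Days 32 and 33 are late, 2 of 7.
- Cut-off Day 30: Days 31, 32 and 33 are late, 3 of 7.

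**4. Delayed first dose.** Protocol 5.1.1.1 allows the first dose to be delayed according to INR. If the origin were the first dose and Visit 4 stayed tied to Visit 2, the late days would be:

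| Delay | Cut-off (elapsed / Day 1 counted) | Late days of 7 |
|---|---|---|
| 1 day | Day 32 / Day 31 | 1 / 2 |
| 2 days | Day 33 / Day 32 | 0 / 1 |
| 3 days | Day 34 / Day 33 | 0 / 0 |

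The result depends on the origin, so the origin has to be stated.

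**5. Where does a late scan go?** Protocol 6.4 tells families that "medication should not be taken on the day of visit 4".
- Last dose the day before Visit 4: scan = stop + 1, inside stop + 2, so treatment-emergent.
- Last dose on Day 30 and scan on Day 33: scan = stop + 3, so post-treatment.

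For a child who completes treatment, a late scan falls in one of these two analyses if its condition is met. The condition refers to a confirmed recurrent event. SAP 3.3 uses recurrent for symptomatic VTE and names asymptomatic deterioration separately, as does Protocol 7.5. Whether deterioration alone meets the condition is not stated.

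**6. Size of one omitted event.** Assuming the full analysis set has 20 children, 10 per stratum: overall 1/20 = 5% becomes 0/20 = 0%; within a stratum 1/10 = 10% becomes 0/10 = 0%.

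**The case against.** **The SAP may intend to count to Visit 4.** SAP 6.3 first names the end of intended treatment and gives the 30 days only in brackets. SAP 6.3.1 describes its treatment period as running up to Visit 4, and Protocol 6.5 titles Visit 4 the end-of-treatment visit. This stands as evidence of intent. It does not settle the rule, because the SAP 6.3.1 formulas use a fixed 30 and SAP 6.3 states a fixed number of days that a programmer would follow.

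**Exclusion needs the event to be dated to the scan.** This stands as a condition. Neither document gives a dating rule; Protocol 6.14.2 refers CIAC procedures to an adjudication manual that was not supplied.

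**A fixed window has merit.** It gives every child equal follow-up and gives a child without Visit 4 an end date. The fix should keep that. It should also treat both components alike: extending the window only for imaging would count an asymptomatic finding on Day 32 and drop a symptomatic recurrence on the same day.

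**Stronger readings that the documents do not support**
- A reader might take the origin as Visit 1, because the only IxRS row in the current flow chart is there, and conclude that every Visit 4 scan is too late. That row is data entry, and the SAP 4.3 imputation rules would be unreasonable with an assignment date 10 to 60 days before the first dose.
- A reader might infer that the event disappears from the report. For completers that requires the narrow reading of recurrent event.
- A reader might set the Table 9-1 intervals for 0/20 and 1/20 side by side as a changed main result. SAP 6.3 plans proportions, not intervals; Table 9-1 illustrates precision for the sample size.

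**Conclusion.** The mismatch is real and minor. With assignment at Visit 2 and the event dated to the scan, asymptomatic deterioration on a compliant scan on Days 32-33 (or Days 31-33) is left out of the main composite proportion, and the per-protocol repeat does not clearly avoid this.

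The fractions 2/7 and 3/7 are shares of permitted calendar days, not of scans. How many scans would fall there is unknown and could be none: nominal Visit 4 (Day 30) is inside either cut-off, and imaging is done only where applicable. Efficacy is secondary and descriptive, and the primary bleeding analysis is untouched. The 20-child denominator is also an assumption, since 20 is the planned number treated and the full analysis set is all enrolled children except screening failures.

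**What to change.** In SAP 6.3:

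1. Define the origin for rivaroxaban children as the Visit 2 (Day 1) date, state the cut-off as a study day (Day 31 on the elapsed-days reading), and say how a delayed first dose is handled in the analysis.
2. For both components of the composite, end the main window at the later of that cut-off and the child's Visit 4 date when Visit 4 is within its permitted window (to Day 33). Use the fixed cut-off for children without a Visit 4. Footnote the rule in the tables. None of the 7 permitted scan days is then late.
3. State that any confirmed efficacy component, including asymptomatic deterioration, triggers the treatment-emergent and post-treatment analyses.

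The cost is a few sentences, one derivation rule and one footnote, with no new data. The downside is that follow-up differs between children by up to about 3 days (33 − 31 = 2 or 33 − 30 = 3), and the reported incidence may be slightly higher.
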